16.2.1 Patient registration/randomisation procedure

At the point of randomisation participants will be automatically registered on to the trial using the trial screening website. Randomisation is after the online consent, the screening process and after the online baseline assessment. The consent forms on the screening website are available separately to this protocol. There is a two-part consent process which in the first part asks for permission to screen and take part in the assessment. The second part of consent at the end of the baseline assessment asks for agreement that the participant wants to take part in the main study. Participants can stop the assessment at any stage and be emailed a link to return the screening website. This allows them to have time to consider the participant information which they have read on screen and which is emailed to them. The email link will be live for 14 days. After this time the participant will need to contact the site to ask for the link to be reset.

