- In the consent (a) questionnaire the information sheet will be presented in selected language and consent form with fields for completion. Consent A asks for consent to take part in the assessment for the trial. Recruits will be asked for their contact details during the consent process and if consent is given then they can screen for eligibility. The recruit will automatically be emailed a copy of the information sheet, the privacy policy and the consent form for their records.
- In the baseline assessment, potential recruits will be presented with a series of questionnaires
 designed to see if the trial is right for them/they meet eligibility criteria. Those excluded will be
 automatically routed to pages detailing why, with links to sources of help. There will be pages
 tailored for current/past depression, suicide risk, mania/psychosis and these (downloadable)
 pages will be in the language for the appropriate country. It is hoped that having been provided
 with the option to self-screen out with depression in the pre-screening phase of assessment that
 very few people will screen out for depressions or risk during assessment.
- Those meeting eligibility criteria will be asked to complete a series of questionnaires designed to assess their emotional competence so they are funnelled into the appropriate trial. The trial they enter will based on cut-offs on the emotional competence assessment measures (see 6 above).
- Participants will be asked to complete further questionnaires to learn more about their current mental and emotional wellbeing, behaviours, views and environment so that the research teams can learn more about what predicts wellbeing, poor mental health and the response to the different self-help versions of the app.
- Participants will be asked demographic questions regarding their gender, ethnicity, occupation, parent's occupation and schooling.
- At the end of the baseline assessment, non-excluded participants will be asked to consent to take part in the trial.
- Participants can at any time during the assessment save what they have done and will have been emailed when they gave consent A so that they can complete their assessment in stages. The link is live for 2 weeks so they have that long to complete the assessment and read the materials before consenting to take part in the trial (consent b). Two weeks was chosen as some of the

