questionnaires ask about well-being in the last 2 weeks so if the time period was longer, those results would be out of date.

- When the participant has completed their assessment, a trigger is sent to the CTU database which signals it to collect all the participant's data through the Qualtrics API.
- When participants consent to take part in the trial participants will be allocated (using the trial allocation algorithm) in to one of the 2 cmRCT trials (as detailed in the inclusion and exclusion criteria) and randomised into one of the 3 conditions: usual practice plus personalized digital emotional competence (EC) self-help (the novel experimental intervention), usual practice plus digital CBT self-help (active control) and usual practice including self-monitoring (the usual practice control condition).
- Consenting participants will automatically be signed up to use the app via an API. MSS will be sent their email address, the language and which condition they are randomised to. The MSS account number will collected and stored with the trial number on the EXCTU website so these accounts can always be linked.
- The MONSENSO data management system will then email the participant a link so that they can set a password and download the app.
- Participants will complete their version of the self-help app completing general mood and emotion monitoring and, where provided, receiving tips, strategies and advice for promotion and prevention through self-reflective and learning exercises, watching animations, reading texts, listening to sound clips, answering quizzes and tests. There is no measurement of risk or symptoms on the app but there will be a help menu available at all times with helpful information for their country and the contact details of the site researcher. The app does not provide diagnosis, features intended to calculate clinical risk or clinical decisions, or features intended to influence an actual treatment. There is no communication with a therapist.
- If participants choose to use the audio recording feature on the app then acoustic features extracted from the voice files on the smart phone and their masked and de-identified (randomly -spliced) voice files will be encrypted and sent securely to collaborators AUD.

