Young people will be initially routed to or seek out the study website and after age screening will be provided with the participant information sheet (which will be submitted with the protocol), consent form A and data protection policy to review on the screening website. There will be a check box at the bottom of the information sheet which participants will need to check before they can sign the consent form. Participants will then be asked to read, date and electronically sign consent form A and provide their contact details. Consent form A asks for consent to undertake the assessment and confirmation that the participation understands the nature of the study (the consent forms will be submitted for review with this protocol). When consent is given they will automatically be emailed a copy of the consent form, information sheet and data protection /privacy policy. The recruit will then be asked to complete background screening measures to determine eligibility on the online screening website. Non-excluded recruits can stop and save their assessment at any time and be emailed a link to return to the assessment. The participant will have 2 weeks in which to be able to return to their part completed assessment. After this time they would need to start the assessment again if they wanted to take part.

If a participant completes the baseline assessment and is eligible for the cohort and trial then they will be presented with consent form B which asks them to consent to taking part in the trial. Recruits are advised that they can take time to consider taking part and can save their assessment whilst they do so. Our Youth Advisory Board advised us that most recruits would probably want to continue and gain access to their App at this stage and would be discouraged by having to wait. There is therefore an option for the participants to consent to take part in the cohort/trial at the end of the assessment. On completion of consent form B participants are advised that our App developer MSS will be emailing them a link to access their App and when their next follow up is due. At this stage the recruit is randomised and be given a unique participant trial number.

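### Protocol 16.2.1 has the site reset an expired baseline link where 7.2 requires a restart, so PHQ-9 and suicidality answers could be more than two weeks old at randomisation

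*Protocol*

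**What the plan says.** Three places in the protocol deal with an applicant who stops part-way through the baseline assessment.

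- **Section 7 (Trial procedures)** sets the time limit: "The link is live for 2 weeks so they have that long to complete the assessment and read the materials before consenting". It gives the reason as well, namely that certain "questionnaires ask about well-being in the last 2 weeks so if the time period was longer, those results would be out of date".
- **Section 7.2 (Consent)** repeats the limit, "The participant will have 2 weeks in which to be able to return to their part completed assessment", and states what follows expiry: "After this time they would need to start the assessment again if they wanted to take part".
- **Section 16.2.1 (Patient registration/randomisation procedure)** describes the same facility: "Participants can stop the assessment at any stage and be emailed a link to return the screening website". The duration is the same, "The email link will be live for 14 days", but the step after expiry is not: "After this time the participant will need to contact the site to ask for the link to be reset".

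Section 16.2.1 says nothing about voiding saved answers, asking any questionnaire again, or limiting the number of resets. SAP section 3.7 takes randomisation to follow directly on baseline data collection, and the SAP sets no maximum age for baseline answers.

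**The concern.** The protocol gives two operating rules for one event, and only one of them contains the safeguard that section 7 justifies. Site staff working from 16.2.1 could reopen a saved assessment after 14 days without departing from that section.

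The answers at issue have two uses. First, PHQ-9 (with LIDAS) and active suicidality are exclusion criteria in both trials (Protocol 6.2). Under Appendix 16.1, a positive reply to any of the three baseline risk questions, each covering the last two weeks, excludes the applicant. Someone whose state changed after answering could therefore be randomised without being asked again. Second, the baseline score is a covariate in the regression for each continuous outcome (Protocol 10.3.2; SAP 6.3). For PREVENT, baseline PHQ-9 is also the reference point for the binary improvement and deterioration outcomes (SAP 6.1.1).

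**Working it through.** The plan states no figure on this point, so the check compares texts and counts days.

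**1. The rules side by side**

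| Protocol section | Time limit | After expiry | Saved answers |
|---|---|---|---|
| 7 | 2 weeks | not stated, but the reason for the limit is given | not stated |
| 7.2 | 2 weeks | assessment is begun again | superseded by the new start |
| 16.2.1 | 14 days | site resets the link on request | not stated |

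The limits agree. The steps after expiry do not.

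**2. What a reset most naturally means**

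- In 16.2.1 the link is the way back for someone who stopped part-way. Sections 7 and 7.2 describe saving progress and returning to it. Resetting such a link suggests restoring that route.
- Section 13.5 says applicants cannot be prevented from re-entering the web address and returning to the screener. A blank restart would therefore not need the site's help.

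Both points favour resumption, but no passage states it.

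**3. Which answers would be old**

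- The measures table in section 3.7 puts WEMWBS, LIDAS, and PHQ-9 with its conditional risk questions before the end-of-screening line. The emotional competence measures follow. Someone who stops during the later measures has normally answered PHQ-9 already.
- The schedule in 16.4 places the wellbeing and depression assessment at screening and not at baseline, with the next at 1 month. Eligibility is assessed at screening only. The table treats screening and baseline as simultaneous, and no second PHQ-9 is scheduled before randomisation.
- PHQ-9 has a stated two-week recall (3.1 and Table 13). So do the baseline risk questions (Appendix 16.1). Table 13 gives no recall period for WEMWBS. LIDAS is asked for the last 3 months and ever (section 3.7 table).

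**4. Maximum age at randomisation**

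Under sections 7 and 7.2 the maximum is 14 days. Under 16.2.1, assume that a reset reopens the saved record and that each reset gives another 14 days. After *k* resets:

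maximum age = 14 × (*k* + 1) days

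- *k* = 1: 14 × 2 = 28 days
- *k* = 2: 14 × 3 = 42 days
- no limit on *k* is stated

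If a reset means a blank restart, the maximum stays at 14 days and the sections agree.

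**5. Effect on the comparison**

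The age of the baseline answers is fixed before allocation, so it cannot depend on arm and gives no reason to expect between-arm bias. For precision, let a fraction *f* of participants have an older baseline, with residual variance *v*₁ instead of *v*₀. The average residual variance rises by the proportion *f* × (*v*₁/*v*₀ − 1). The documents give neither *f* nor *v*₁, so no figure can be attached. The rise is small whenever resets are few.

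**The case against.** The strongest reply is that there may be no conflict. Section 7.2 could be saying what the applicant must do (start again) and 16.2.1 whom to contact for a working link. Section 16.2.1 never says that saved answers survive. On that reading nothing exceeds 14 days, and the limit in sections 7 and 7.2 governs throughout. This stands as a possibility. It is why the consequence must be stated conditionally, and also why the text needs a clarifying sentence.

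Three further replies have weight.

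- Sections 7 and 7.2 already accept up to 14 days between screening answers and the second consent, so some change of state before randomisation is tolerated under either rule. Only the extra interval is at issue.
- PHQ-9 and the risk questions are asked again at 1 month. That helps monitoring but does not correct an eligibility decision already made.
- Section 10.2 describes the last two months of recruitment in the past tense, so a change to the procedure may now reach few applicants. The count for those already randomised does not depend on this.

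A reader might also infer more than the documents support:

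- **That applicants are in fact being randomised on old answers.** The documents do not say what a reset does or how often one occurred.
- **That the protocol itself treats WEMWBS answers as expired after two weeks.** Section 7 refers to well-being in general and names no instrument, and Table 13 gives WEMWBS no recall period.
- **That LIDAS answers expire too.** Its recall periods are far longer than two weeks.
- **That the treatment estimates are biased or materially less precise.** Step 5 of the check gives no ground for bias, and the documents offer no basis for a precision figure.

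**Conclusion.** The point holds as an unreconciled procedure with a conditional consequence. Section 16.2.1 gives a different rule after expiry from 7.2 and omits the safeguard for which section 7 gives the reason. If a reset reopens the saved record, PHQ-9 and suicidality answers could be older than their own two-week recall period at randomisation. They could reach 28 days after one reset and 42 after two if each adds 14 days.

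Both conditions are assumptions. The first is the better reading of the text; the second is for illustration. The number of people affected cannot be estimated from the documents and may be small. The main risk is misclassified eligibility, meaning someone randomised who would have been excluded if asked again. Any loss of precision is probably negligible, a judgement that rests on resets being uncommon.

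**What to change.** 1. Reconcile Protocol 16.2.1 with sections 7 and 7.2: a link reset after 14 days clears the saved answers, and the assessment, including PHQ-9 and its risk questions, is started again.
2. For those already randomised, report the distribution of days from baseline PHQ-9 and WEMWBS to randomisation, and how many exceed 14. WEMWBS belongs in this report because it sits in the same screening block and is the baseline covariate for the PROMOTE primary outcome.
3. Flag a restart after an expired link as such, so that it is not confused with the repeat applications that SAP 6.8 treats as protocol violations.

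The cost is a wording change, a survey setting and one descriptive table. The downside is that a few applicants may not be willing to repeat the questionnaires. If recruitment has closed, item 2 is what remains useful, and it would show whether the gap mattered.

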16.2.2 Data management

There is a separate data management plan which accompanies this trial protocol which gives greater detail.

All data collected within the framework of the study will be pseudo-anonymised and securely stored at a central location under the responsibility of the study sponsor (UNEXE). The conduct of the project will comply with the Directive 95/46/EC of the European Parliament and of the Council of Europe dated 24th October 1995 on the protection of individuals with regard to the processing of personal data and on the free movement of such data, and with the new regulation Regulation (EU) 2016/679 (http://ec.europa.eu/justice/dataprotection/reform/files/regulation_oj_en.pdf) that will replace it and with 1997/66/CE on the handling of personal information and Directive 2002/58/CE (on the same subject). It will comply with regulations transposing this directive at the national level (e.g. Data Protection Act (DPA) number g0027154 in the UK; Bundesdatenschutzgesetz (BDSG) in Germany; "Privacywet" KB 13/02/2001 & KB 17/12/2003 in Belgium).

No data will be collected or used without the explicit informed consent of the participants

During the project, the team will stipulate any conclusive needs within the project regarding participants' data. This may refer to the temporariness of data storage, security of data transfer, relevant consent applications and relevant advertisement of the use of the data. In order to safeguard the confidentiality

of the participants' personal information, such data will be stored in a record that will be kept locked in the institution. Only the researchers will be aware of this personal information. For research purposes each participant will be given a numerical code (to be used in place of a name). The technology should cater for the fact that each participant will be given a unique identification code, rather than a name, and all data will be securely stored and preserved, both electronically and on paper.

Only authorized research personnel will have access to the password protected electronic database. No unauthorized access will be possible. A separate list linking codes with names will be kept in a secure place. The data will be introduced and analysed by computers. As for Internet use and monitoring by means of mobile apps, data protection systems will be designed (using secure passwords, encryption, etc.). The researchers will have access to the database using a password. Also, in order to protect all information, we will follow the AES (Advanced Encryption Standard) strategies for personal password use and data encryption. The study researchers will promise to not reveal data from which personal and health information about the participants could be deduced. The same principles will be taken into consideration in the dissemination of data in the publication of scientific papers and the presentation of research reports at scientific conferences. Monsenso hosts and operates its solution on encrypted servers within the EU. The system complies with the EU 2000/58/EC & 2002/58/EC Directive on privacy and electronic communications and the EU Directives 95/46/EC and with the superseding directive 2016/679 GDPR (and Danish Act on Processing of Personal Data implementing EU Directive 95/46/EC). In terms of the Directive 95/46/EC, Monsenso is to be considered a Data Processor, as are the recruitment sites in ECoWeB, and University of Exeter as sponsor will be considered Data Controller. Data Processing agreements between Monsenso and sites and the data controller will be made, stipulating in what manner Monsenso should process data for the purpose of the ECoWeB project.

Database infrastructure: The ECoWeB project will build a distributed electronic database (managed by UNEXE, Partner 1) during the project that will store all the downloaded cohort data and clinical trial data. Within the clinical trials, UNEXE will be in charge of the set-up and management of the database. The equivalent of anonymised electronic Case Report Form (eCRF) data will be set-up and entered in a data management system, which is fully validated. The eCRF and associated database will be automatically populated from the responses entered by participants via websites and app platform: data will be encrypted and anonymised before downloading from the website or app and then stored securely and converted into an electronic database suitable for analysis. A data manager will be appointed to build and manage the database infrastructure. Data will be routinely backed-up during and after the project to ensure the availability of all the information.

Data Management Plan: The Data Management Plan for the trial will be produced as a deliverable at month 16 for all collected data (demographic, behavioural data). The Data Management Plan will describe how the data will be exploited, checked, shared, curated and preserved. Thus, the procedure for granting access will be detailed and the mechanisms to access the data after the project will be described. The ownership of data generated during the project will be described in the Consortium Agreement.

Data format and types: Standard data formats will be used during the project. Data types will include Volunteer data: Demographics, information provided by participants on questionnaires and on EC assessment instruments.

Data exploitation: All information will have a digital format that will be handled in accordance with European and national data protection regulations. A mechanism to request access, mine, exploit, reproduce or disseminate data generated in the framework of this project will be put in place. After successful evaluation by the ECoWeB consortium, access to the project data may be granted to other parties, following rules that will be defined in a specific agreement between the partners and third parties.

16.2.5 Data protection/confidentiality

A common privacy and data protection policy has been drafted. This is so that participants will not need to re-read new policies from moving from screener to App to Audeering website when common GDPR standards will apply. For this sample of young adults aged 16-22, it was also important that the data protection policy should be in an easily readable format avoiding legalise. The trial data protection and privacy policy can be found below:

16.2.6 Trial documentation and archiving

The materials for the trial will be submitted with this study protocol.

16.3 Authorisation of participating sites

Each site will be authorised after ethical approval has been given by the relevant ethics committee for that site and a data transfer agreement is in place between the site and the UNEXE data controller. Site visits (including remote checks) will be conducted by the trial manager to check that sites are adequately staffed, staff researchers have access to a clinical adviser, and that site staff are familiar with the standard operating procedures, risk assessment procedures and that GCP and GDRP standards will be followed.

16.3.1 Required documentation

Before recruitment can begin at sites, staff CV's and evidence of good clinical practice and GDPR training will be collected. Each site will be provided with copies of the standard operating procedures for the trial. Each site will create a resource of online links and local and national services for those indicating that they have current depression, suicide risk, mania and psychosis. These links will be checked before the trial starts and at monthly intervals during recruitment to ensure that these details are kept up to date.

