We note that the ECoWeB researchers are not clinicians and cannot provide therapy. However, we can guide you in accessing help, for example, by contacting your GP, which is why we ask for GP details. The ECoWeB team are only available during normal working hours, Monday to Friday and may take 1 or 2 working days to respond.

FORM TO SUBMIT

Name

Address

Phone number

GP Name

GP Phone number

GP Address

2) Assessment Website at Follow-up (1 month, 3 month, 12 months)

A recruit may indicate risk on the assessment website in follow-up assessments in response to questions about suicidality. If the participant scores 1-3 on question 9 of the PHQ9, then further questions to assess risk will automatically be presented

PHQ9Q9

Over the last two weeks, how often have you been bothered by any of the following problems? Thoughts that you would be better off dead, or of hurting yourself in some way?

Those scores would represent the answers several days (1), more than half the days (2) and nearly every day (3)

The further risk questions which will automatically be asked:

R1 In the last 2 weeks have you been experiencing regular thoughts about suicide?

R2 In the last 2 weeks have you had any intention to hurt or kill yourself?

R3 In the last 2 weeks have you made any plans to harm yourself or end your life?

If the recruit answers yes to any of those questions then they would continue in the trial and would be automatically presented with the following risk page (for UK):

Screening Website Automated Risk Message at Follow up:

"Your responses to these questions suggest you have been thinking about suicide or about hurting yourself.

These kinds of thoughts can vary a lot. This may have just been a brief passing thought or reflect a sense of feeling trapped, but without any intention to do anything. These thoughts are relatively common and not that unusual in people who feel stressed. If you would like support with these thoughts, please contact your GP or relevant medical professional;

If you feel at high risk to yourself or others, please contact your GP immediately.

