- The **Samaritans [name]** Freephone (UK and Republic of Ireland): [name] (24 hours),offer a confidential service so you can talk about your feelings, you can contact them at www.samaritans.org, Email: [contact]
- **SANE** offers support to anyone coping with mental illness, including concerned relatives or friends. The SANE helpline **[name]** is available 7 days a week from 6.pm-11 pm
- **Maytree** is a registered charity supporting people in suicidal crisis and is open for calls and emails 24 hours a day. [name], [contact]
- Young Minds Crisis Messenger provides free, 24/7 crisis support across the UK if you are experiencing a mental health crisis. If you need urgent help text YM to [name]. Texts are free from EE, O2, Vodafone, 3, Virgin Mobile, BT Mobile, GiffGaff, Tesco Mobile and Telecom Plus.
- CALM [name] (Daily 17:00-midnight) Offers support to young men in the UK who are down
 or in a crisis, www.thecalmzone.net
- **ChildLine**, Freephone 24h helpline: **[name]** If you're under 19 you can confidentially call, email, or chat online about any problem big or small, www.childline.org.uk. You can sign up for a childline account on the website to be able to message a counsellor anytime without using your email address and can Chat 1:1 with an online advisor
- **The Mix**, Freephone: [name] (13:00-23:00 daily), If you're under 25 you can talk to The Mix for free on the phone, by email or on their webchat. You can also use their phone counselling service, or get more information on support services you might need. www.themix.org.uk

Talking to people who understand can make it much easier to manage your symptoms so **please do** call your GP or one of the specialist helplines above.

For participants reporting significant levels of depression at any of the follow-up assessments (defined as PHQ-9 score >20) – the follow-up website will automatically provide them with the following information:

Follow-up Website Automated message for depression

"Your responses to these questions suggest that within the last month, your overall mood has been low for at least 2 weeks and has had a negative effect on your life. It may be that you are currently experiencing an episode of depression or going through a period of stress or loss.

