Pls/supervisors/clinicians (e.g., local psychiatrists or clinical psychologists) will also familiarise themselves with this SOP and provide researchers with their contact details in case the researcher needs advice. When clinical academic staff are away on leave they should ensure appropriate cover is arranged to support researcher with advice on for any risk issues that might arise in their absence. The clinician is available to support and guide the researcher in responding to risk and where requested in communicating and providing guidance to the participant.

We note that guidance on depression and suicide including general advice, signposting for help, websites and telephone lines (as for webpages noted above) are also provided within the help section within all versions of the App.

Telephone contact

When conducting telephone interviews in which risk may be disclosed, the interviewer should establish the telephone number and location of the participant at the start of the call, and clarify the boundaries of confidentiality:

'Hi, is that (name) this X from the ECoWeb trial, is now a convenient time to talk?' [or in response to answering a call direct from a participant – at which point we would ask for name and email, so we can identify them]

If yes 'This call is confidential and the only reason I would break that is if I thought you were at risk to yourself or others and it was in your best interests. .

We just wanted to give you a call after your message to us in the email you sent / I would like to clarify what you are telling me now on the phone.

Can I just check where you are at the moment? [obtain details of location/address]

"I see that you've said / you mentioned that....... (examples: if thoughts of death /"what is the point?" / "it might be better if I did not wake up",

"Has this gone as far as thinking about harming yourself or killing yourself?" If yes, or if already stated:

'These are common thoughts and can vary a lot in their severity and it's important to make sure you are receiving the right kind of support. So I would now like to ask you some more questions that will explore these feelings in a little more depth."

INTENTION

Have you had any intention to hurt or kill yourself? YES OR NO

1 Do you know how you would kill yourself? If **yes – ask for and record** details Yes / No

2 Have you made any actual plans to end your life? If yes – ask for and record details	Yes / No

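### The stated check of help links ends with recruitment, about 12 months before the last follow-up risk page and app help menu that use such links

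*Protocol*

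**What the plan says.** Protocol 16.3.1 sets the task: "Each site will create a resource of online links and local and national services for those indicating that they have current depression, suicide risk", with mania and psychosis also on the list. The timing follows: "These links will be checked before the trial starts and at monthly intervals during recruitment". The stated purpose is to keep the details current.

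Signposting of this kind is used well beyond recruitment:

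- **Suicide-risk page.** Protocol 16.1 describes follow-up screening at 1, 3 and 12 months. For a participant who answers yes to any of the risk questions, "they would continue in the trial and would be automatically presented with the following risk page".
- **Depression page.** Protocol 16.1 shows a page of websites and helplines at any follow-up where the PHQ-9 score is above 20.
- **App help menu.** Protocol 7 says "there will be a help menu available at all times with helpful information for their country". The risk SOP in 16.1 adds that depression and suicide guidance, with websites and telephone lines, "are also provided within the help section within all versions of the App". Under Protocol 13.11 the app stays open to participants for at least the 12 months they are in the trial.

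Protocol 16.1 makes advice and signposting the default response to a possible clinical presentation. The trial provides no medical care and does not routinely hold GP details.

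**The concern.** The protocol treats these contacts as needing monthly verification, and its own pre-screening help page warns that healthcare arrangements may change because of COVID-19. That reason does not lapse when the last participant is randomised. The pages then stay in use in four countries for about another year, and participants who indicate risk at that stage remain in the trial.

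What is at stake is the upkeep of a participant-safety measure. No endpoint, estimate or sample-size figure is affected.

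**Working it through.** **1. The plan's own timeline.**

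- Recruitment, R: up to 52 weeks, about 12 months (Protocol 10.2).
- Last follow-up, F: 12 months after randomisation (Protocol 7.8).
- Stated trial period: 24 months from start of recruitment to final follow-up (Protocol Table 6).

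R + F = 12 + 12 = 24 months, which reproduces the stated period.

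**2. Length without a stated check.** After the check before the start, required checks run from month 0 to month R. The last participant's final assessment is due at month R + F. The gap is (R + F) − R = F = 12 months, or 12/24 = half of the planned period. Its length does not depend on R.

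**3. Which scheduled assessments fall in the gap.** Assuming uniform accrual over R months, the share of month-k assessments due after recruitment closes is min(1, k/R).

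| Recruitment length assumed | 1 month | 3 months | 12 months |
|---|---|---|---|
| 9 months (lower end in SAP 5.3) | 1/9 = 11% | 3/9 = 33% | 100% |
| 12 months (Protocol 10.2) | 1/12 = 8% | 3/12 = 25% | 12/12 = 100% |
| 18 months (illustration of overrun) | 1/18 = 6% | 3/18 = 17% | 12/18 = 67% |

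Protocol 10.2 reports faster recruitment in the last 2 months. That would raise the 1- and 3-month shares and leave the 12-month share at 100% on a 12-month recruitment. These are shares of scheduled assessments before attrition. They do not count risk pages shown or links that failed.

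**4. Where each set of contacts is used, and what else stands behind it.**

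| Place | In use until | Stated check | Route not dependent on the links |
|---|---|---|---|
| Screening and exclusion pages | End of recruitment | Whole period | Not at issue |
| Follow-up suicide-risk page | Last 12-month follow-up | To end of recruitment at most | Automated record to the chief investigator, logged by the trial manager and passed to the site; a clinician may make contact; contact form |
| Follow-up page for PHQ-9 above 20 | Last 12-month follow-up | To end of recruitment at most | No form on the page as printed; 16.1 says in general terms that elevated symptom risk is logged and the site informed |
| App help menu | At least 12 months after randomisation | To end of recruitment at most | Site researcher's contact details; the app measures no risk or symptoms, so it raises no alert |

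The words 'at most' are needed because 16.3.1 does not say which pages its resource feeds. If it was written for screening alone, the follow-up pages and the app have no stated check at any time.

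**5. Search for a check elsewhere.** The monitoring text in Protocol 12 and 13.7 covers data, systems and processes, and 8.11 covers app use and technical problems. None of these mentions the help links.

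**The case against.** The strongest reply is that the links are one layer among several. At follow-up, a positive suicide-risk answer sends a record to the chief investigator and the site, and a trial clinician may contact the participant (16.1). Site teams hold contact details for that purpose (13.7), and each site has a designated senior clinician (section on adverse events). The follow-up risk page carries a form that reaches the team and asks for GP details. The UK version of that page also lists the GP, NHS 111, the emergency department, family or friends, and eight named services, so one stale entry would not empty it. Contacts would have been checked up to the close of recruitment, so any decay starts from there.

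Much of this stands, and it keeps the point minor. It does not remove it. Clinician contact is optional, and the form is answered in working hours, possibly after 1 or 2 working days. The detailed alert is tied to the suicide-risk questions rather than to the PHQ-9 threshold or the app.

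A second reply is that Protocol 12 refers to a monitoring plan and manual, and 16.1 to a risk register updated through the project. Link checks might continue there. Those documents are not available here, so the finding is limited to what the protocol and SAP state.

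A reader might go further and infer that participants at risk will be sent to dead contacts, or that the safeguard fails. The documents do not support this. They report no failed link and give no failure rate, and the other routes remain. Nor should the shares in the first table be averaged into one percentage of affected risk screens. That would assume equal completion at every follow-up, whereas Protocol 7.8 allows for 40% loss at 3 months and Protocol 3.4 expects relatively high attrition by 12 months.

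**Conclusion.** The point holds as a minor gap in an operational safety procedure. As written, 16.3.1 leaves about 12 of the 24 planned months without a stated check of the help contacts. Essentially all 12-month assessments fall in those months. The 12-month length follows from the follow-up schedule alone. The statement about 12-month assessments assumes that recruitment lasts no more than about 12 months, and with a longer recruitment some would fall inside the checked period.

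The exposure is least cushioned on the depression page and in the app help menu. The likely consequence is that contacts could become outdated without anyone being required to notice.

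**What to change.** In Protocol 16.3.1, replace the recruitment-only timing with monthly checks from the start of recruitment until the last participant's 12-month follow-up, and keep the check before the trial starts. State that the check covers the follow-up suicide-risk page, the follow-up depression page and the app help menu as well as the screening pages, in each site's language. If the monitoring manual already requires this, a cross-reference to it is enough.

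The cost is one amended sentence and about 12 further short monthly rounds by site researchers, who already chase follow-ups (Protocol 5). The change alters no clinical rule and no risk procedure. It only keeps current the contacts on which the protocol already relies.
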